17.3 FREQUENCY OF VISITS

To ensure that the study is conducted in accordance with the terms of the clinical protocol, study monitors must visit each investigational site at routine intervals throughout the duration of the study. The exact frequency of visits shall be determined on an individual site basis as detailed in the Clinical Monitoring Plan, and shall depend upon the following factors:

- Rate of subject enrollment
- Experience of the Investigator in conducting clinical studies
- Record of previous site compliance

18. AUDITS AND INSPECTIONS

Participation as an Investigator in this study implies acceptance of potential inspection by government regulatory authorities. The Investigator must also be prepared to permit study-related audits and inspections by the Sponsor, CRO, EC and the site's institutional compliance and quality assurance

CONFIDENTIAL Page **58** of **67** groups. The Investigator will ensure the capability for inspections of applicable study-related facilities, records, and reports.

The investigators will be available to the Sponsor, EC or other regulatory authorities to discuss study issues as requested. All involved parties must keep the subject data strictly confidential.

In the event that an Investigator is contacted by a Regulatory Agency in relation to this clinical trial/investigation, the Investigator will notify the Sponsor immediately and IEC as appropriate.

19. STATISTICAL METHODS

19.1 ANALYSIS SETS

The analysis data sets will be defined in a way that mirrors the Superion P140004 study.

The primary analysis cohort for this study will be the Modified Intent-to-Treat Cohort, defined as: Modified Intent-to-treat patient population (mITT): The mITT patient population will include all patients having an anesthesia start time. Subjects with an anesthesia start time but that do not receive the device will be failures.

Confirmatory analysis will be performed in the Per Protocol Cohort, defined as: Per protocol (PP) Population: The PP patient population will include all subjects with 12-month follow-up data and no major protocol deviations and subjects that failed before 12 months

19.2 PRIMARY ENDPOINT

Subjects will be evaluated at the 12-month follow-up for the primary endpoint.

Effectiveness success will be evaluated as a two-prong composite endpoint:

- ZCQ Responder (at least two of the three ZCQ domains)
 - $\circ \geq 0.5$ point improvement in physical function.
 - $\circ \geq 0.5$ point improvement in symptom severity
 - Mean satisfaction ≤ 2.5 points.
- No secondary surgical intervention (SSI) including re-operations, revision, removals or supplemental fixation or clinically significant confounding treatments (i.e., epidural steroid injections at the index level, spinal cord stimulators or rhizotomies) through 12 months.

The primary effectiveness hypothesis is that the composite success rate for the Lobster device is larger than the performance goal of 61.1%. A detailed description of the how the performance goal was calculated will be provided in the statistical analysis plan (SAP).

Formally, the hypotheses to be tested are:

H₀: The expected proportion of patients with composite success at Month 12 (p_T) is less than or equal to the performance goal (PG) of 61.1%.

CONFIDENTIAL Page **59** of **67** H_A: The expected proportion of patients with composite success at Month 12 (p_T) is greater than the performance goal (PG) of 61.1%.

These hypotheses may be symbolically represented as:

H_o:
$$p_T \le PG = 61.1\%$$

H_A: $p_T > PG = 61.1\%$

Where p_T is the composite success rate for subjects treated with the Lobster device.

A one-sided normal approximation binomial test with type 1 error set to α =0.05 will be used to demonstrate that the investigational device meets the performance goal.

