1. STUDY SUMMARY

Study Full Title	Evaluation of Safety and Effectiveness of Lobster Dynamic Interspinous Spacer in Lumbar Spinal Stenosis: A Single Arm, Prospective, Mutli-Center Study
Study Sponsor	Diametros Medical srl
Study Number	LB2CT01
Protocol Version and Date	1.0, 08-09-2022
STUDY OVERVIEW	
Study Design	Prospective, multi-center study of the Lobster System in patients with moderate lumbar spinal stenosis.
Purpose	To demonstrate the safety and effectiveness of the Lobster device in comparison to an SSED-based performance goal.
Expected Study Duration	2 years, including enrollment and post-operative follow-up
Number of Subjects & Sites	Estimated 210 investigational subjects in up to 3 sites in Italy will be enrolled.
Treatment	All enrolled subjects will be assigned to treatment with the Lobster device
Evaluation Schedule	 Subjects will be evaluated at the following timepoints: Pre-operation 6 weeks 3 months 6 months 12 months 24 months, and annual thereafter until final subject reaches 12 months
ELIGIBILITY CRITERIA	
Intended Subject Population	Lobster Implantable Dynamic Interspinous Device is indicated to treat skeletally mature patients suffering from pain, numbness, and/or cramping in the legs (neurogenic intermittent claudication) secondary to a diagnosis of moderate lumbar spinal stenosis, with or without Grade 1 spondylolisthesis, confirmed by X-ray, MRI and/or CT evidence by a thickened ligamentum flavum, narrowed lateral recess, and/or central canal or foraminal narrowing. Patients must also meet all study inclusion and none of the study exclusion criteria.
Main Inclusion Criteria	meet all of the following criteria:

1. Male or female subjects \geq 45 years of age.
2. Persistent leg/buttock/groin pain, with or without back
pain, that is relieved by flexion activities (example:
sitting or bending over a shopping cart).
3. Subjects who have been symptomatic and undergoing
conservative care treatment for at least 6 months.
4. Diagnosis of degenerative spinal stenosis of the
lumbar spine, defined as the narrowing of the midline
sagittal spinal canal (central) and/or narrowing
between the facet superior articulating process (SAP),
the posterior vertebral margin (lateral recess), and the
nerve root canal (foraminal).
5. Radiographic confirmation of at least moderate spinal
stenosis which narrows the central, lateral, or
foraminal spinal canal at one or two contiguous levels
from L1-L5. Moderate spinal stenosis is defined as

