19.3 SAMPLE SIZE ASSESSMENT

The sample size was determined in order to have at least as many subjects as the Superion arm in the P140004 study, which enrolled 190 subjects, and to show superiority to the performance goal calculated from the results of that study.

The pooled two-prong composite effectiveness at Month 12 in the P140004 study was 71.1%, so the reference rate is specified as 0.711. The reference margin is set to be 10%, which is the same non-inferiority margin used in the Superior study. The performance goal is then 71.1%-10%=61.1%.

The sample size was calculated assuming the same success in the Lobster arm that was seen in the Superion study, 71.1%. With type 1 error set to α =0.05 and power=85%, the study would need to enroll 162 subjects. Allowing for 15% loss to follow-up, the study would need to enroll at least 191 subjects.

This study will enroll a minimum of 191 subjects and a maximum of 250 subjects. The final sample size will be justified in the SAP.

Expected distribution of enrollment among site is: 50% Cagliari (main site), 25% Siena, 25% Catania. The enrollment cap for the main site is 105 patients.

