19.6 MISSING DATA/SENSITIVITY ANALYSIS

Handling of missing data will be described in the SAP.

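### Does the normal-approximation binomial test fail to hold the one-sided 5% error rate that Section 19.2 states?

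*Protocol*

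**What the plan says.** Section 19.2 tests whether the 12-month composite success rate exceeds 61.1%, by "A one-sided normal approximation binomial test with type 1 error set to" 0.05. It names neither the variance form nor a continuity correction.

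Section 19.3 derives the goal: "The performance goal is then 71.1%-10%=61.1"%. It assumes a true rate of 71.1%. "With type 1 error set to α =0.05 and power=85"%, "the study would need to enroll 162 subjects"; a 15% allowance for loss to follow-up raises this to 191. It then states: "This study will enroll a minimum of 191 subjects and a maximum of 250 subjects". The Study Summary puts the expected number at 210: "Estimated 210 investigational subjects in up to 3 sites in Italy will be enrolled".

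Section 19.1 makes the mITT set primary: "The mITT patient population will include all patients having an anesthesia start time". Section 19.6 says of incomplete data only: "Handling of missing data will be described in the SAP".

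**The concern.** With one arm and a fixed goal, the exact probability of a false success can be computed, so an approximation is not needed. At the two enrolment figures that stand out, the minimum of 191 and the expected 210, that probability is above 5% if every enrolled subject is analysed, and the mITT definition makes such an analysis conceivable. At 128 of 191, or 140 of 210, the test would declare success while the exact one-sided 95% lower limit (60.99% or 60.92%) lies just below 61.1%. The sentence in Section 19.2 also does not exclude a statistic with the observed variance (Wald), whose size at 162 is 6.14%. If the excess were systematic, the only confirmatory claim of the study would rest on a test more liberal than stated.

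**Working it through.** **Inputs.** Goal p0 = 0.611, assumed rate p1 = 0.711, one-sided α = 0.05, power 85%, loss 15% (Sections 19.2 and 19.3); enrolment 191 to 250 (Section 19.3), expected 210 (Study Summary).

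**1. The plan's own sample size.** With the null variance for α and the alternative variance for power,

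n = [(1.645 × √(0.611 × 0.389) + 1.036 × √(0.711 × 0.289)) / 0.10]² = 161.7, so 162.

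162 / 0.85 = 190.6, so 191. Both figures reproduce. The other usual formulas do not give 162: alternative variance only 148, null variance only 171, continuity-corrected 172. The calculation therefore points to the uncorrected test with the null variance (the score form).

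**2. Cut-off and exact size of the score form.** Success is declared at the smallest count r with

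(r − n × 0.611) / √(n × 0.611 × 0.389) > 1.645.

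For n = 191: mean 116.70, standard deviation 6.738, threshold 127.78, so r = 128. The exact size is P(X ≥ 128 | n = 191, p = 0.611) = 5.34%. In the same way, with power taken at p = 0.711:

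| Analysed | Score cut-off | Size | Power | Exact-test cut-off | Size | Power |
|---|---|---|---|---|---|---|
| 162 | 110 | 4.38% | 83.8% | 110 | 4.38% | 83.8% |
| 163 | 110 | 5.45% | 86.5% | 111 | 3.86% | 82.5% |
| 178 | 120 | 4.81% | 87.8% | 120 | 4.81% | 87.8% |
| 191 | 128 | 5.34% | 90.6% | 129 | 3.88% | 87.7% |
| 200 | 134 | 4.95% | 91.1% | 134 | 4.95% | 91.1% |
| 210 | 140 | 5.56% | 93.1% | 141 | 4.11% | 90.9% |
| 250 | 166 | 4.81% | 95.5% | 166 | 4.81% | 95.5% |

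The 162 is what remains of 191 after the planned loss; 178 is 85% of 210 (178.5).

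**3. Is there a drift above 5%?** Over every possible number analysed:

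| Range analysed | Test | Mean size | Minimum | Maximum | Sizes above 5% |
|---|---|---|---|---|---|
| 162 to 190 | score | 4.87% | 4.17% | 5.69% | 12 of 29 |
| 191 to 250 | score | 4.92% | 4.22% | 5.67% | 26 of 60 |
| 162 to 190 | exact | 4.24% | 3.60% | 4.94% | 0 of 29 |
| 191 to 250 | exact | 4.33% | 3.70% | 4.996% | 0 of 60 |

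The score form swings on both sides of 5% and averages slightly below it. The cause is discreteness: moving the cut-off by one success changes the size by about 1.2 to 1.8 points in this range, so no whole-number rule can sit at 5% throughout. The expected variance of the count under the null, n × 0.611 × 0.389, is 38.5 at 162 and 45.4 at 191, which is ordinary ground for a normal approximation.

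**4. What turns on it.** At 191 only the count 128 separates the two tests, and at 210 only 140. Under the goal these counts have probability 1.5% and 1.4%; under 71.1%, 2.9% and 2.2%. The exact lower limits fall short of 61.1% by 0.11 and 0.18 points.

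**The case for a change.** The strongest counter-argument is that Section 19.2 itself fixes the primary test and does not leave it to the SAP, that an exact test is available at no computational cost, and that it holds 5% at every number analysed from 162 to 250. A sponsor seeking registration would avoid a success that the exact limit contradicts. All of that is true, and a statistician who values guaranteed size may well choose the exact test.

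It shows an alternative, though, not a mistake, and the alternative has costs. Its average size lies further from 5% (4.33% against 4.92% over 191 to 250). It takes power from above the planned 85% to below it at 163, 166, 169, 171 and 172 analysed, with the lowest value 82.5% at 163. At 162 and 178 it changes nothing. It would also have to fit the missing-data method, which Section 19.6 leaves to the SAP: with multiple imputation there is no single whole-number count to which an exact limit applies.

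The Wald argument is arithmetically right: at 162 that form accepts 109 successes, with size 6.14%, and over 191 to 250 its size exceeds 5% at 47 of 60 numbers. But the protocol nowhere names that form, its sample size reproduces only with the null variance in the α term, and the choice of variance estimator is a detail that an SAP ordinarily supplies.

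**Conclusion.** The concern does not hold. Section 19.2 names an approximate test, so its 5% is a nominal level, and the form consistent with Section 19.3 keeps close to it: sizes from 4.17% to 5.69% over 162 to 250 analysed, with averages just under 5%. The values above 5% at 191 and 210 are correct, but they require that nobody is missing, and they are two points on an oscillating curve; 200 and 250 give 4.95% and 4.81%. After the planned 15% loss the size is below 5% and the exact test has the same cut-off.

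This rests on three assumptions: the null-variance statistic without continuity correction, a single binomial count with no imputed outcomes, and independent subjects with a common success rate. If the SAP chose the observed-variance form, the average size would rise to about 5.4% to 5.5%, with a maximum of 6.38% at 170 analysed. That would be a matter for the SAP; the protocol does not state it.

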19.3 SAMPLE SIZE ASSESSMENT

The sample size was determined in order to have at least as many subjects as the Superion arm in the P140004 study, which enrolled 190 subjects, and to show superiority to the performance goal calculated from the results of that study.

The pooled two-prong composite effectiveness at Month 12 in the P140004 study was 71.1%, so the reference rate is specified as 0.711. The reference margin is set to be 10%, which is the same non-inferiority margin used in the Superior study. The performance goal is then 71.1%-10%=61.1%.

The sample size was calculated assuming the same success in the Lobster arm that was seen in the Superion study, 71.1%. With type 1 error set to α =0.05 and power=85%, the study would need to enroll 162 subjects. Allowing for 15% loss to follow-up, the study would need to enroll at least 191 subjects.

This study will enroll a minimum of 191 subjects and a maximum of 250 subjects. The final sample size will be justified in the SAP.

Expected distribution of enrollment among site is: 50% Cagliari (main site), 25% Siena, 25% Catania. The enrollment cap for the main site is 105 patients.

19.4 SAFETY ANALYSES

Assessment of the safety of the investigational implant will include an evaluation of the incidence and severity of complications and adverse reactions associated with the treatment. Adverse event rates will be summarized by type of AE and for specific AEs in two ways: 1) per patient incidence of specific AEs and classes of AEs and 2) by event, summarizing event counts by visit interval over time and in accordance with FDA Guidance. Device and procedure-related events will be summarized by severity and relatedness. Events listings that include details such as relatedness, severity, onset and resolution status will be provided for all events and relevant subsets of events such as serious events and related events. Primary safety comparisons will be performed using the mITT analysis set. The summary tables will show the adverse events (in coded terms), the total number of events, and the number and the percentage of subjects affected in each treatment group ("subject wise evaluation") and stratified by relation to device and severity.

CONFIDENTIAL Page 60 of 67 The event rates observed in the Superion SSED (P140004) will be used as clinical guideposts only. There is no formal statistical hypothesis test on these endpoints. Please note that the primary endpoint captures both safety and effectiveness, and therefore these events are considered interesting but appropriately evaluated in this framework. Additional details regarding the safety comparisons will be provided in the SAP.

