	29. Involved in pending litigation of the spine or worker's compensation related to the back.
	30. Enrolled in the treatment phase of another drug or
	device clinical investigation (currently or within past 30 days).
	31. Congenital defect of the spine.
	32. Pregnant or lactating.
	33. Any further contraindications and limitations of the
	device as described in the instructions for use (IFU).
STUDV ENDPOINTS	
	Subjects will be evaluated at the 12 month follow up for the
	primary endpoint
	printing endpoints
	Efficacy success will be evaluated as a two-prong composite
Primary Endpoint	endpoint:
Lindey Endpoint	• ZCQ Responder (at least two of the three ZCQ
	domains)
	$\circ \ge 0.5$ point improvement in physical function. $\circ \ge 0.5$ point improvement in symptom severity
	• Mean satisfaction <2.5 points.

	 No secondary surgical intervention (SSI) including reoperations, revision, removals or supplemental fixation or clinical significant confounding treatments (i.e., epidural steroid injections at the index level, spinal cord stimulators or rhizotomies) through 12 months. Safety success will be evaluated using precision-based statistics to characterize the incidence of major device- or procedure-related complications, including: Device integrity failure (dislodgement, migration, or deformation). New or persistent worsened neurological deficit at the index level. Spinous process fractures. Deep infection, death, or other permanent device attributed disability. 		
Secondary Endpoints	 Oswestry Disability Index (ODI) Visual Analogue Scale (VAS) (Back and Leg) SF-12 Short Form Survey (Physical Function and Mental Health) Patient satisfaction survey Neurologic status 		
STATISTICAL CONSIDERATIONS			
Sample Size	Mimimum of 191 subjects- maximum of 250 subjects		
Primary Effectiveness Hypothesis	The primary effectiveness hypothesis is that the composite success rate for the Lobster device is larger than the performance goal of 61.1%.		
Compliance statement	This investigation will be conducted in compliance with the CIP, the current version of the Declaration of Helsinki, ISO14155, ICH-GCP (as far as applicable) as well as all national legal and regulatory requirements.		

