6. STUDY OBJECTIVES

6.1 PRIMARY OBJECTIVES

The primary objective of this study is to demonstrate the safety and effectiveness of the Lobster device in comparison to an SSED-based performance goal (PG). This clinical study is a prospective, multi-centered study with a historical control designed to support future international regulatory registrations

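### The protocol promises to demonstrate safety against a performance goal, but its only goal (61.1%) concerns effectiveness and no safety test is planned

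*Protocol*

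**What the plan says.** **The promise.** The Purpose in the Study Summary is "To demonstrate the safety and effectiveness of the Lobster device in comparison to an SSED-based performance goal". Section 6.1 sets the same aim as the primary objective.

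**The goal.** Section 19.3 starts from a rate for the earlier interspinous device trial: "The pooled two-prong composite effectiveness at Month 12 in the P140004 study was 71.1" per cent. It subtracts a 10-point margin to reach 61.1%. Section 19.2 then states: "The primary effectiveness hypothesis is that the composite success rate for the Lobster device is larger than the performance goal of 61.1" per cent. The composite has two prongs: ZCQ response on at least two of three domains, and no secondary surgical intervention or listed confounding treatment through 12 months.

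**Safety.** The Study Summary and section 7.4 say: "Safety success will be evaluated using precision-based statistics to characterize the incidence of major device- or procedure-related complications". The list covers device integrity failure, new or persistently worsened neurological deficit at the index level, spinous process fracture, deep infection, death and other permanent device-attributed disability. No threshold is attached. Section 19.4 says that these endpoints have no formal hypothesis test and that the historical event rates serve only as clinical guideposts. It adds that "the primary endpoint captures both safety and effectiveness, and therefore these events are considered interesting but appropriately evaluated in this framework".

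**The concern.** The objective and the analysis disagree. The objective announces a demonstration of safety against a goal. The analysis sections contain no safety goal and rule out a safety test. The term *safety success* suggests a criterion, but what follows is a description of incidence, which can neither succeed nor fail.

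The sentence in 19.4 is offered as the link between the two. If it is accepted, a composite rate above 61.1% could be read, under the Purpose and 6.1, as having demonstrated safety, although that result carries no inference on the complications the protocol itself names as its safety measure. Section 6.1 says the study is meant to support regulatory registrations, and section 21.7 names a premarket approval supplement, so the wording of the objective fixes what will be claimed.

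**Working it through.** **1. Does any safety quantity enter the test or the sample size?** The inputs in 19.2 and 19.3 are p0 = 0.611, p1 = 0.711, one-sided alpha = 0.05, power = 85% and 15% loss to follow-up.

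n = [(z₀.₉₅·√(p0(1−p0)) + z₀.₈₅·√(p1(1−p1))) / (p1−p0)]²

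= [(1.645 × 0.4875 + 1.036 × 0.4533) / 0.10]² = 161.7, rounded up to 162.

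162 / 0.85 = 190.6, rounded up to 191.

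The protocol's 162 and 191 reproduce exactly from effectiveness inputs alone. The sample size is not in dispute; no safety rate or limit plays any part in it.

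**2. What does meeting the goal require?** The normal-approximation test is passed when the observed rate exceeds 0.611 + 1.645·√(0.611 × 0.389 / n).

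| n | Critical rate | Successes needed | Failures allowed |
|---|---|---|---|
| 162 | 67.4% | 110 | 52 |
| 191 | 66.9% | 128 | 63 |

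Nothing in this rule refers to the listed complications.

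**3. Can a listed complication occur in a composite success?** Set the safety list in 7.4 beside the ways a subject can fail the composite:

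- a secondary surgical intervention or listed confounding treatment (19.2);
- ZCQ non-response, judged by "ZCQ Responder (at least two of the three ZCQ domains") (19.2);
- non-receipt of the device, since in the mITT set "Subjects with an anesthesia start time but that do not receive the device will be failures" (19.1).

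Device integrity failure, neurological deficit, spinous process fracture and deep infection are not themselves components. Each causes failure only if it leads to one of the three routes above. A fracture or migration that leads to none of them is counted as a success. How a death or a missing 12-month ZCQ is counted is left to the SAP and is no part of this point.

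Section 3.3 shows why this matters for this device. It reports 11.3% complications (spinous process fractures and bone remodelling) in the device-only group of an earlier cohort, alongside marked ZCQ improvement in both groups. These are group-level data and do not show that the same patients had both.

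**4. What can the design say about safety?** It can give an incidence with an interval. The protocol states no 12-month rate for the listed set, so the event counts below are assumptions from 0 to about 12%. The top count for each n is the whole number nearest to 11.3% of n. That figure also includes bone remodelling, which is not on the list. Intervals are exact (Clopper-Pearson) 95%.

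| Events / n | Observed | 95% interval |
|---|---|---|
| 0 / 191 | 0% | 0 to 1.9% |
| 10 / 191 | 5.2% | 2.5 to 9.4% |
| 19 / 191 | 9.9% | 6.1 to 15.1% |
| 22 / 191 | 11.5% | 7.4 to 16.9% |
| 18 / 162 | 11.1% | 6.7 to 17.0% |
| 28 / 250 | 11.2% | 7.6 to 15.8% |

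**The case against.** Four arguments can be made for the protocol.

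- **The sentence in 19.4 may refer to the whole of 7.4.** That section lists both the composite and the safety events under primary endpoints, so the primary endpoint would literally include both. But 19.2, under the heading for the primary endpoint, lists only the composite. On either reading there is still no safety goal or test to support the Purpose and 6.1.
- **The composite is partly a safety measure.** This stands: any reoperation, revision, removal or supplemental fixation is a failure, and so is non-receipt of the device. In the retrospective study described in 3.3, three dislocations were treated by retrieval and a new implant, and one procedure was abandoned because of a spinous process fracture. All four would be composite failures here. Those are 6-month retrospective data in which 172 patients had cement augmentation of the spinous processes, so they do not show that the composite catches every listed event. No section documents a listed complication in a composite success; the gap follows from the definitions.
- **The statistical text is candid.** It calls the hypothesis one of effectiveness and says openly that safety is untested. This also stands, and it is why the objective needs to be brought into line with it.
- **Details are left to the SAP.** Only additional details are. The objective and the absence of a test are both fixed in the protocol, and an SAP cannot rewrite the objective.

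Descriptive safety is a legitimate choice in a single-arm device study. The fault lies in the mismatch.

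**Conclusion.** The concern holds. The Purpose and 6.1 claim a demonstration of safety against a goal that the design does not contain, and the bridging sentence in 19.4 does not supply it. The safety-related prong covers only complications that lead to reintervention or a listed treatment. Meeting 61.1% therefore puts no limit on listed complications that leave the composite a success.

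The inconsistency is one of wording, with no numerical size and no effect on the test or the sample size. It does change what the trial may conclude about safety: an estimate of complication incidence, with an interval about 10 points wide at 162 evaluable subjects (17.0 − 6.7 = 10.3) and about 8 points at 250 (15.8 − 7.6 = 8.2), if the rate is near 11%. The conclusion itself rests only on the protocol's definitions; the widths rest on the assumed rate.

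**What to change.** - **Study Summary (Purpose) and 6.1:** limit the performance-goal comparison to effectiveness and say that safety is estimated.
- **Study Summary (Primary Endpoint) and 7.4:** replace *safety success* with a primary safety estimate: the per-patient incidence of the listed major complications through 12 months in the mITT set, with a 95% confidence interval whose method is given in the SAP.
- **19.4:** delete the sentence that the primary endpoint captures both aspects, and call the primary safety analyses summaries, not comparisons.
- **Optional:** add a descriptive mITT table of composite success together with freedom from every listed complication. It should not be compared with 61.1%, because that goal was derived from the two-prong rate.

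The cost is wording in five places and at most one extra table from data already collected. The downside is a weaker safety claim, an estimate with an interval in place of a demonstration. If the sponsor wishes to keep the stronger claim, the protocol would have to prespecify and justify a safety goal or an upper confidence limit for the listed complications.
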